9.0 AGENT INFORMATION

9.1 Entinostat

[figure not shown]
(SNDX-275, MS-275, NSC#706995, [REDACTED]), NCI-supplied agent

9.1.1 Structure and molecular weight

Chemical name: 3-Pyridylmethyl N-{4-[(2-aminophenyl)carbamoyl]benzyl} carbamate

Molecular formula: C₂₁H₂₀N₄O₃

Structural formula:

Molecular weight: 376.41

Mechanism of action: Entinostat inhibits to a family of enzymes called histone deacetylases (HDACs) that regulate chromatin remodeling and gene transcription via the dynamic process of acetylation and deacetylation of core histones. Entinostat inhibits histone deacetylases, changes chromatin configuration, and induces differentiation and apoptosis of cancer cells through an epigenetic mechanism.

9.1.2 Supplied by:

Entinostat is supplied by Syndax Pharmaceuticals, Inc. and distributed by DCTD, NCI.

9.1.3 Formulation

The agent is supplied as a 1 mg (pink to light red, in bottles of 40), or 5 mg (yellow, in bottles of 40) film-coated tablets (round-biconvex). Each tablet also contains mannitol, carboxymethyl starch sodium, hydroxypropyl cellulose, potassium bicarbonate, and magnesium stearate. The film coating consists of hydroxypropyl methylcellulose, talc, titanium dioxide, and ferric oxide pigments (red and yellow).

9.1.4 Storage

Store the bottles at room temperature (15-30°C), and protect from light. Tablets may be dispensed in pharmacy amber dispensing bottles with storage at a temperature equal or below 15-30°C (59-86°F; do not freeze) with an expiration period of 30 days from the date of repackaging.

9.1.5 Stability

Shelf life stability studies of the intact bottles are on-going. Tablets dispensed in pharmacy amber dispensing bottles should have an expiration date of 30 days from the date of repackaging.

9.1.6 Administration

Administer orally, on an empty stomach, at least 1 hour before or 2 hours after a meal. Tablets should be swallowed whole and not split, crushed or chewed. If a patient vomits within 30 minutes after the dose of entinostat is administered, that dose may be repeated. If the patient vomits more than 30 minutes after administration of entinostat, the dose will be considered as having been taken, and administration should resume with the subsequent regularly scheduled dose.

9.1.7 Drug interactions

No formal drug interaction studies have been performed in humans. Data from in vitro experiments showed that, while entinostat inhibited cytochrome P-450 enzymes 2B6 and 3A4, the degree of the inhibition make it unlikely that any *in vivo* systemic interactions would occur. Intestinal CYP 3A4 may be inhibited by entinostat. However, entinostat did not inhibit any UGT enzymes tested. In addition, entinostat was found to induce CYP 1A2, CYP 2C6, and CYP 2B8 as well as UGT 1A4. Finally, entinostat is a substrate for P-glycoprotein (P-gp) and breast cancer resistance protein (BCRP) transporters.

9.1.8 Entinostat Toxicities

The Comprehensive Adverse Events and Potential Risks list (CAEPR) provides a single list of reported and/or potential adverse events (AE) associated with an agent using a uniform presentation of events by body system. In addition to the comprehensive list, a subset, the Specific Protocol Exceptions to Expedited Reporting (SPEER), appears in a separate column and is identified with bold and italicized text. This subset of AEs (SPEER) is a list of events that are protocol

specific exceptions to expedited reporting to NCI (except as noted below). Refer to the 'CTEP, NCI Guidelines: Adverse Event Reporting Requirements' http://ctep.cancer.gov/protocolDevelopment/electronic_applications/docs/aeguidelines.pdf for further clarification. *Frequency is provided based on 215 patients.* Below is the CAEPR for MS-275 (SNDX-275, entinostat).

NOTE: Report AEs on the SPEER **ONLY IF** they exceed the grade noted in parentheses next to the AE in the SPEER. If this CAEPR is part of a combination protocol using multiple investigational agents and has an AE listed on different SPEERS, use the lower of the grades to determine if expedited reporting is required.

Version 2.5, September 10, 2018¹

Adverse Events with Possible Relationship to MS-275 (SNDX-275, entinostat) (CTCAE 5.0 Term) [n= 221]			Specific Protocol Exceptions to Expedited Reporting (SPEER)
Likely (>20%)	Less Likely (<=20%)	Rare but Serious (<3%)	
BLOOD AND LYMPHATIC SYSTEM DISORDERS			
Anemia			Anemia (Gr 3)
GASTROINTESTINAL DISORDERS			
	Abdominal pain		Abdominal pain (Gr 2)
	Constipation		Constipation (Gr 2)
	Diarrhea		Diarrhea (Gr 3)
	Dyspepsia		Dyspepsia (Gr 2)
Nausea			Nausea (Gr 3)
Vomiting			Vomiting (Gr 3)
GENERAL DISORDERS AND ADMINISTRATION SITE CONDITIONS			
	Edema limbs		Edema limbs (Gr 2)
Fatigue			Fatigue (Gr 3)
	Fever		Fever (Gr 2)
INFECTIONS AND INFESTATIONS			
	Infection ²		Infection ² (Gr 3)
INVESTIGATIONS			
	Alkaline phosphatase increased		Alkaline phosphatase increased (Gr 2)
	Lymphocyte count decreased		Lymphocyte count decreased (Gr 4)
Neutrophil count decreased			Neutrophil count decreased (Gr 4)
Platelet count decreased			Platelet count decreased (Gr 4)
	White blood cell decreased		White blood cell decreased (Gr 3)
METABOLISM AND NUTRITION DISORDERS			
Anorexia			Anorexia (Gr 3)
	Dehydration		Dehydration (Gr 2)
	Hyperglycemia		Hyperglycemia (Gr 2)

Adverse Events with Possible Relationship to MS-275 (SNDX-275, entinostat) (CTCAE 5.0 Term) [n= 221]			Specific Protocol Exceptions to Expedited Reporting (SPEER)
Likely (>20%)	Less Likely (<=20%)	Rare but Serious (<3%)	
Hypoalbuminemia			Hypoalbuminemia (Gr 2)
	Hypocalcemia		Hypocalcemia (Gr 2)
	Hypokalemia		Hypokalemia (Gr 2)
	Hyponatremia		Hyponatremia (Gr 3)
Hypophosphatemia			Hypophosphatemia (Gr 3)
MUSCULOSKELETAL AND CONNECTIVE TISSUE DISORDERS			
	Myalgia		Myalgia (Gr 2)
NERVOUS SYSTEM DISORDERS			
	Dysgeusia		Dysgeusia (Gr 2)
Headache			Headache (Gr 2)
RESPIRATORY, THORACIC AND MEDIASTINAL DISORDERS			
	Cough		Cough (Gr 2)
	Dyspnea		Dyspnea (Gr 3)
SKIN AND SUBCUTANEOUS TISSUE DISORDERS			
		Erythema multiforme	

¹This table will be updated as the toxicity profile of the agent is revised. Updates will be distributed to all Principal Investigators at the time of revision. The current version can be obtained by contacting [contact]. Your name, the name of the investigator, the protocol and the agent should be included in the e-mail.

²Infection includes all 75 sites of infection under the INFECTIONS AND INFESTATION SOC.

³Gastrointestinal hemorrhage includes Anal hemorrhage, Cecal hemorrhage, Colonic hemorrhage, Duodenal hemorrhage, Esophageal hemorrhage, Esophageal varices hemorrhage, Gastric hemorrhage, Hemorrhoidal hemorrhage, Ileal hemorrhage, Intra-abdominal hemorrhage, Jejunal hemorrhage, Lower gastrointestinal hemorrhage, Oral hemorrhage, Pancreatic hemorrhage, Rectal hemorrhage, Retroperitoneal hemorrhage, and Upper gastrointestinal hemorrhage under the GASTROINTESTINAL DISORDERS SOC.

Adverse events reported on MS-275 (SNDX-275, entinostat) trials, but for which there is insufficient evidence to suggest that there was a reasonable possibility that MS-275 (SNDX-275, entinostat) caused the adverse event:

BLOOD AND LYMPHATIC SYSTEM DISORDERS - Febrile neutropenia; Hemolysis; Leukocytosis

CARDIAC DISORDERS - Atrial fibrillation; Atrioventricular block complete; Cardiac disorders - Other (transient right-side heart failure with worsening tricuspid regurgitation); Chest pain - cardiac; Conduction disorder; Heart failure; Left ventricular systolic dysfunction; Palpitations; Pericardial effusion; Pericarditis; Sinus tachycardia; Supraventricular tachycardia; Ventricular fibrillation

EAR AND LABYRINTH DISORDERS - Hearing impaired

EYE DISORDERS - Blurred vision

GASTROINTESTINAL DISORDERS - Anal mucositis; Colitis; Dysphagia; Enterocolitis; Esophageal pain;

Esophagitis; Flatulence; Gastrointestinal disorders - Other (hyperdefecation); Gastrointestinal hemorrhage³; Hemorrhoids; Mucositis oral; Pancreatitis; Periodontal disease; Rectal mucositis; Rectal pain; Small intestinal mucositis; Typhlitis; Visceral arterial ischemia

GENERAL DISORDERS AND ADMINISTRATION SITE CONDITIONS - Chills; Edema face; Generalized edema; Injection site reaction; Multi-organ failure; Non-cardiac chest pain; Pain

IMMUNE SYSTEM DISORDERS - Allergic reaction; Anaphylaxis; Autoimmune disorder

INJURY, POISONING AND PROCEDURAL COMPLICATIONS - Bruising

INVESTIGATIONS - Activated partial thromboplastin time prolonged; Alanine aminotransferase increased; Aspartate aminotransferase increased; Blood bilirubin increased; CPK increased; Creatinine increased; GGT increased; INR increased; Investigations - Other (coagulopathy); Investigations - Other (vitamin D deficiency); Lipase increased; Serum amylase increased; Weight loss

METABOLISM AND NUTRITION DISORDERS - Acidosis; Hypercalcemia; Hyperkalemia; Hypermagnesemia; Hyponatremia; Hypertriglyceridemia; Hyperuricemia; Hypoglycemia; Hypomagnesemia; Tumor lysis syndrome

MUSCULOSKELETAL AND CONNECTIVE TISSUE DISORDERS - Arthralgia; Back pain; Bone pain; Chest wall pain; Generalized muscle weakness; Muscle cramp; Musculoskeletal and connective tissue disorder - Other (thorax pain); Myositis; Pain in extremity

NEOPLASMS BENIGN, MALIGNANT AND UNSPECIFIED (INCL CYSTS AND POLYPS) - Tumor pain

NERVOUS SYSTEM DISORDERS - Ataxia; Depressed level of consciousness; Dizziness; Dysphasia; Intracranial hemorrhage; Neuralgia; Olfactory nerve disorder; Peripheral motor neuropathy; Peripheral sensory neuropathy; Seizure; Syncope; Tremor

PSYCHIATRIC DISORDERS - Anxiety; Confusion; Depression; Insomnia; Libido decreased

RENAL AND URINARY DISORDERS - Acute kidney injury; Proteinuria; Renal and urinary disorders - Other (bladder distension); Renal calculi; Renal hemorrhage; Urinary frequency; Urinary retention

RESPIRATORY, THORACIC AND MEDIASTINAL DISORDERS - Allergic rhinitis; Atelectasis; Epistaxis; Hypoxia; Laryngeal mucositis; Pharyngeal mucositis; Pleural effusion; Pleuritic pain; Pulmonary edema; Respiratory failure; Tracheal mucositis

SKIN AND SUBCUTANEOUS TISSUE DISORDERS - Alopecia; Hyperhidrosis; Nail loss; Photosensitivity; Pruritus; Purpura; Rash maculo-papular; Skin and subcutaneous tissue disorders - Other (hyperkeratotic lesions/squamous cell carcinoma); Urticaria

SURGICAL AND MEDICAL PROCEDURES - Surgical and medical procedures - Other (packed RBC transfusion)

VASCULAR DISORDERS - Flushing; Hypertension; Hypotension; Thromboembolic event

Note: MS-275 (SNDX-275, entinostat) in combination with other agents could cause an exacerbation of any adverse event currently known to be caused by the other agent, or the combination may result in events never previously associated with either agent.

9.2 Agent Ordering and Agent Accountability

NCI supplied agent may be requested by the eligible participating investigator (or their authorized designee) at each participating institution. The CTEP assigned protocol number must be used for ordering all CTEP supplied investigational agents. The responsible investigator at each participating institution must be registered with CTEP, DCTD through an annual submission of FDA form 1572 (Statement of Investigator), NCI Biosketch, Agent Shipment Form, and Financial Disclosure Form (FDF). If there are several participating investigators at one institution, CTEP supplied investigational agents for the study should be ordered under the name of one lead participating investigator at that institution.

Submit agent requests through the PMB Online Agent Order Processing (OAOP) application. Access to OAOP requires the establishment of a CTEP Identity and Access Management (IAM) account and the maintenance of an “active” account status, and a “current” password, and active person registration status. For questions about drug orders, transfers, returns, or accountability, call or email PMB any time. Refer to the PMB’s website for specific policies and guidelines related to agent management.

In general, sites may order initial agent supplies when a subject is being screened for enrollment onto the study.

9.3 Agent Inventory Records

The investigator, or a responsible party designated by the investigator, must maintain a careful record of the receipt, dispensing and final disposition of all agents received from the PMB using the appropriate NCI Investigational Oral Agent (Drug) Accountability Record (DARF) available on the CTEP forms page. Store and maintain separate NCI Investigational Agent Accountability Records for each agent, strength, formulation and ordering investigator on this protocol.

9.4 Investigator Brochure Availability

The current versions of the IB for the agent will be accessible to site investigators and research staff through the PMB Online Agent Order Processing (OAOP) application. Access to OAOP requires the establishment of a CTEP Identity and Access Management (IAM) account and the maintenance of an “active” account status, a “current” password and active person registration status. Questions about IB access may be directed to the PMB IB coordinator via email.

10.0 CRITERIA FOR REMOVAL FROM PROTOCOL THERAPY AND OFF STUDY CRITERIA

10.1 Criteria for Removal from Protocol Therapy

- a) Clinical (including physical examination or serum tumor markers) or radiographic evidence of progressive disease (See [Section 12.0](#)).
- b) Adverse Events requiring removal from protocol therapy (See [Section 5.2](#) [Section 6.0](#)).
- c) Refusal of protocol therapy by patient/parent/guardian
- d) Non-compliance that in the opinion of the investigator does not allow for ongoing participation.
- e) Physician determines it is not in the patient's best interest.
- f) Repeated eligibility laboratory studies (CBC with differential, bilirubin, ALT (SGPT) or serum creatinine) are outside the parameters required for eligibility prior to the start of entinostat (See [Section 8.1](#)).
- g) Study is terminated by Sponsor.
- h) Pregnancy.

Patients who are removed from protocol therapy during cycle 1 should continue to have the required observations in [Section 8.1](#) until the originally planned end of the cycle or until all adverse events have resolved per [Section 13.4.4](#), whichever happens LATER. The only exception is with documentation of the patient's withdrawal of consent. Patients who are removed from protocol therapy in subsequent cycles should have the necessary observations to ensure adequate clinical care.

Patients who are off protocol therapy are to be followed until they meet the criteria for Off Study (see below). Ongoing adverse events, or adverse events that emerge after the patient is removed from protocol therapy, but within 30 days of the last dose of investigational agent, must be followed and reported via RAVE and CTEP-AERS (if applicable). Follow-up data will be required unless consent is withdrawn.

10.2 Off Study Criteria

- a) Thirty days after the last dose of the investigational agent.
- b) Death
- c) Lost to follow-up
- d) Withdrawal of consent for any required observations or data submission.
- e) Enrollment onto another COG therapeutic (anti-cancer) study
- f) The fifth anniversary of the date the patient was enrolled on this study.
- g) The patient does not receive protocol treatment after study enrollment.

11.0 STATISTICAL AND ETHICAL CONSIDERATIONS

11.1 Sample Size and Study Duration

A minimum of 4 patients will be enrolled in this study. The expected maximum number of evaluable patients required to estimate the MTD/RP2D is 12. Once the MTD or recommended Phase 2 dose has been defined, up to 6 additional patients with recurrent or refractory solid tumors may be enrolled to acquire PK data in a representative number of young patients (i.e. patients < 12 years old). Therefore, a maximum of 22 patients are expected to be enrolled which allows for 6 patients at each of 2 dose levels, 6 additional patients enrolled at the MTD/RP2D for PK analysis, and a 20% inevaluable rate. Review of the enrollment rate into previous COG new agent studies indicates that 1-2 patients per month are available, which will permit completion of the study within 11-22 months. An absolute maximum of 36 patients is anticipated in the unlikely scenario that each of 2 dose levels is expanded to 12 patients due to different classes of AEs, 6 additional patients are enrolled at the MTD for PK analysis, and a 20% inevaluable rate. The absolute maximum would require about 18-36 months for completion.

11.2 Definitions

11.2.1 Evaluable For Adverse Events

Any patient who receives at least one dose of the study drug(s) and who experiences a dose-limiting toxicity is considered evaluable for Adverse Events. In addition, for the dose-escalation portion during Cycle 1, patients must receive at least 85% of the prescribed dose per protocol guidelines and must have the appropriate toxicity monitoring studies performed to be considered evaluable for dose limiting toxicity. Patients who do not have DLT and are not considered evaluable for toxicity will be replaced.

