5.0 TREATMENT PROGRAM

5.1 Overview of Treatment Plan

		Entinostat oral	Action
Week 1	Day 1	X	
Week 2	Day 8	X	
Week 3	Day 15	X	
Week 4	Day 22	X	
End of Cycle	Day 28		Evaluation

Entinostat will be administered orally on Days 1, 8, 15, and 22 of a 28-day cycle. Patients may continue to receive entinostat for up to 5 years.

Drug doses should be adjusted based on the BSA calculated from height and weight measured within 7 days prior to the beginning of each cycle. If a patient vomits within 30 minutes after the dose of entinostat is administered, that dose may be repeated. If vomiting occurs greater than 30 minutes after the administered dose, the dose will not be repeated. If a patient misses an entinostat dose and less than 12 hours have passed since the scheduled dosing time, that dose should be taken immediately. If a patient misses an entinostat dose and more than 12 hours have passed since the scheduled dosing time, this dose will be skipped. If a patient accidentally takes an extra dose during a day, the next scheduled dose of entinostat will be skipped.

The patient/family will be asked to complete a Patient Medication Diary (see [Appendix V](#)).

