11.3 Dose Escalation and Determination of MTD

The rolling six phase 1 trial design will be used for the conduct of this study.³² Two to six patients can be concurrently enrolled onto a dose level, dependent upon (1) the number of patients enrolled at the current dose level, (2) the number of patients who have experienced DLT at the current dose level, and (3) the number of patients entered but with tolerability data pending at the current dose level. Accrual is suspended when a cohort of six has enrolled or when the study endpoints have been met.

Dose level assignment is based on the number of participants currently enrolled in the cohort, the number of DLTs observed, and the number of participants at risk for developing a DLT (i.e., participants enrolled but who are not yet assessable for toxicity). For example, when three participants are enrolled onto a dose cohort, if toxicity data is available for all three when the fourth participant entered and there are no DLTs, the dose is escalated and the fourth participant is enrolled to the subsequent dose level. If data is not yet available for one or more of the first three participants and no DLT has been observed, or if one DLT has been observed, the new participant is entered at the same dose level. Lastly, if two or more DLTs have been observed, the dose level is de-escalated. This process is repeated for participants five and six. In place of suspending accrual after every three participants, accrual is only suspended when a cohort of six is filled. When participants are inevaluable for toxicity, they are replaced with the next available participant if escalation or de-escalation rules have not been fulfilled at the time the next available participant is enrolled onto the study.

The following table provides the decision rules for enrolling a patient at (i) the current dose level (ii) at an escalated dose level, (iii) at a de-escalated dose level, or whether the study is suspended to accrual:

# Pts Enrolled	# Pts with DLT	# Pts without DLT	# Pts with Data Pending	Decision
2	0 or 1	0, 1 or 2	0, 1 or 2	Same dose level
2	2	0	0	De-escalate*
3	0	0, 1 or 2	1, 2 or 3	Same dose level
3	1	0, 1 or 2	0, 1 or 2	Same dose level
3	0	3	0	Escalate**
3	≥ 2	0 or 1	0 or 1	De-escalate*
4	0	0, 1, 2 or 3	1, 2, 3 or 4	Same dose level
4	1	0, 1, 2 or 3	0, 1, 2 or 3	Same dose level
4	0	4	0	Escalate**
4	≥ 2	0, 1 or 2	0, 1 or 2	De-escalate*
5	0	0, 1, 2, 3 or 4	1, 2, 3, 4 or 5	Same dose level

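### The 85% dose rule tolerates no fully omitted weekly dose in Cycle 1, and DLT-free children who miss one because of drug toxicity can be replaced without being shown in the escalation decision

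*Combined protocol and SAP*

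**What the plan says.** **Schedule.** Section 5.1: "Entinostat will be administered orally on Days 1, 8, 15, and 22 of a 28-day cycle". The dose in mg is the same each week. A missed dose is not made up: if "more than 12 hours have passed since the scheduled dosing time, this dose will be skipped".

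**Evaluability.** Section 11.2.1 treats the two kinds of patient differently. With a DLT, one dose is enough: "Any patient who receives at least one dose of the study drug(s) and who experiences a dose-limiting toxicity is considered evaluable for Adverse Events". Without a DLT, in the dose-escalation portion, "patients must receive at least 85% of the prescribed dose per protocol guidelines", and the toxicity monitoring must also have been done.

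**Replacement.** Section 11.2.1: "Patients who do not have DLT and are not considered evaluable for toxicity will be replaced". Section 11.3 adds a condition: "they are replaced with the next available participant if escalation or de-escalation rules have not been fulfilled". Neither section makes an exception according to why the dose was missed.

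**Interruptions outside DLT.** Section 5.5.1.1 states that an allergic reaction forcing the drug to be stopped is not a DLT. The same list, introduced as exclusions from DLT, also contains Grade 2 non-hematological toxicity of 7 days or more that requires interruption of treatment. As printed, that is not a DLT either.

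**Allowance.** Section 11.1 plans for "6 additional patients enrolled at the MTD/RP2D for PK analysis, and a 20% inevaluable rate".

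**The concern.** A threshold of 85% reads as if some shortfall were tolerated. With four equal doses, none is tolerated at the level of whole doses, and the text does not say so. Sites and the study chair could therefore apply it differently.

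The larger issue is which children leave the denominator. A child who had a DLT always counts. A child without one counts only after essentially full dosing. A child whose dose was omitted or stopped for drug toxicity short of a DLT falls between the two and is replaced in the same way as a child who simply forgot a tablet. The DLT fraction behind the decisions in Sections 11.2.2 and 11.3 is then conditional on something close to tolerability, and the cohort is at most six children in the usual case. Nothing requires the number of such children to be shown when the dose decision is made.

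**Working it through.** **1. The plan's own figures.** Section 11.1 allows 6 + 6 + 6 = 18 patients, and 18 × 1.2 = 21.6, which rounds up to 22. The absolute maximum is 12 + 12 + 6 = 30, and 30 × 1.2 = 36. Both stated totals are reproduced, so the 20% was applied as a multiplier on the evaluable number.

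**2. The threshold in whole doses.** The fractions are k/4 = 0, 25, 50, 75 or 100%. The smallest k with k/4 ≥ 0.85 is the next whole number above 0.85 × 4 = 3.4, which is 4. One omitted dose gives 75% at every entry in the dosing nomogram (Appendix IV).

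**3. The threshold in mg.** The rule refers to dose, not to a count of doses. At 4 mg weekly the cycle total is 16 mg and 85% of it is 13.6 mg. A child who took 14 mg has 14/16 = 87.5% and passes; a child who omitted one whole dose has 12/16 = 75% and fails. A dose skipped after an accidental extra dose (Section 5.1) leaves the total at 100%.

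**4. The denominator.** If a dose withheld for toxicity stays in the prescribed total, the child has 3/4 = 75% and is inevaluable. If it is taken out, the child has 3/3 = 100% and counts as a non-DLT. The text does not say which applies.

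**5. How often a missed dose costs evaluability.** Assume independent misses with probability q per dose (the documents give no rate). Then P(inevaluable | no DLT) = 1 − (1 − q)^4:

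| q (assumed) | Inevaluable |
|---|---|
| 2% | 7.8% |
| 5% | 18.5% |
| 10% | 34.4% |

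**6. Effect on the six-patient rule.** Let d be the probability of DLT and t the probability of a DLT-free child missing a dose for drug toxicity (both assumed). The DLT rate is d/(1 − t) if such children are replaced, d if they count as non-DLT, and d + t if they count as intolerant. For a DLT rate p, P(at most 1 in 6) = (1 − p)^6 + 6p(1 − p)^5.

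| d, t (assumed) | DLT rate if replaced | P, replaced | P, as non-DLT | P, as intolerant |
|---|---|---|---|---|
| 10%, 10% | 0.10/0.90 = 11.1% | 0.86 | 0.89 | 0.66 |
| 15%, 15% | 0.15/0.85 = 17.6% | 0.71 | 0.78 | 0.42 |
| 20%, 15% | 0.20/0.85 = 23.5% | 0.57 | 0.66 | 0.32 |

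Replacement makes a dose level slightly harder to pass than counting these children as non-DLT, and clearly easier to pass than counting them as intolerant.

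**The case against.** The strongest reply is that the toxicity route is narrow. Section 6 directs holds only for Grade 4 neutropenia or thrombocytopenia and for non-hematological DLT, and patients whose event is a DLT are evaluable after one dose. Vomiting within 30 minutes allows a repeat dose, and after that the dose counts as taken (Sections 5.1 and 9.1.6). This stands. A reader might infer that the other exclusions in Section 5.5.1.1, such as short Grade 3 fever or infection or electrolyte falls that respond to supplementation, routinely cost a dose. No text directs a hold for them, so any omission would be discretionary and of unknown frequency. The two routes the text itself supplies are allergic discontinuation and the Grade 2 item as printed.

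A second reply is that requiring near-full exposure before a child counts as DLT-free is a defensible, cautious choice. This also stands. A reader might infer that the remedy is to accept three of four doses. That is a trade-off, because it counts the affected children as non-DLT. In the last row of the table the DLT rate falls from 23.5% to 20% and the chance of passing rises from 0.57 to 0.66, so escalation becomes easier.

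Third, these children are not invisible. The study chair is told of dose modifications (Section 6.0), evaluability and DLTs are reviewed on a weekly call with the statistician (Section 14.4.2), and all toxicities are summarized (Section 11.3). That softens the point, but none of these provisions requires the count of toxicity-caused omissions to be set beside the DLT count at the decision.

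**Conclusion.** The point holds as a gap in the definition of evaluability and in what is shown at each decision. It is certain that one fully omitted dose fails the 85% rule, that no exception is written for omission due to toxicity, and that Section 5.5.1.1 as printed leaves some interruptions outside DLT. The size is not known: every miss and skip rate above is an assumption.

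Three stronger readings are not supported:

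- **That the rule means exactly 100%.** This is true for whole doses but not in mg (step 3).
- **That the plan makes a dose look safer than it is.** The direction depends on how these children would otherwise be counted, and the one-third rule in Section 11.2.2 concerns DLT, not completion of Cycle 1.
- **That the 20% allowance is too small.** It covers all enrolled patients, including those added for PK, whereas the 85% rule is written for the dose-escalation portion and the rates in step 5 apply only to DLT-free children. The documents give no miss rate against which to test it.

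**What to change.** In Section 11.2.1:

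- State the threshold as a number of whole Cycle 1 doses (as written it means all four) and say how a partly taken dose is counted.
- Say whether a dose withheld for toxicity stays in the denominator.
- Add that a DLT-free child whose Cycle 1 dose was omitted or stopped for drug-related toxicity may be replaced for the DLT count but stays listed at that dose level. The number of such children is shown beside the DLT count at each escalation decision and for the RP2D.

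In Section 5.5.1.1, reconcile the Grade 2 interruption item with its place in the list of exclusions. Whether those children count as DLT, and so are evaluable after one dose, depends on the answer.

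The cost is a few sentences of text and one extra count in the material for the weekly review in Section 14.4.2. The third item changes neither the DLT count nor the replacement of patients. The downside is a small amount of extra tabulation.
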